8.2 Efficacy Evaluations

Assessment of response will be made using the International Myeloma Working Group response criteria (Palumbo et al, 2014). All patients' files and radiologic images must be available for source verification.

Imaging may include chest, abdomen and pelvis CT or MRI or PET/CT scans (when applicable); brain CT or MRI scan for patients with known CNS involvement; bone scan and/or bone x-rays for patients with lytic bone lesions, if applicable.

Tumor assessments conducted at baseline, at the end of every other cycle, whenever disease progression is suspected (e.g., symptomatic deterioration), and at the time of withdrawal from the study (if not done in the previous 6 weeks).

The same imaging technique used to characterize each identified and reported lesion at baseline will be employed in the following tumor assessments.

Assuming a background ORR of 10%, if the ORR on the current study for patients receiving ONC201 were 30% or higher there would be interest in further investigation of this treatment regimen. Therefore, this study will be used to detect a difference of 20% using a one- sided binomial test. Statistically, the hypothesis that will be tested is:

$H_0: p \leq 0.1$ versus $H_1: p > 0.3$

where p is the proportion of patients achieving an objective response. Enrollment of 30 patients will yield 84% power to detect a 20% difference at an alpha level of 0.05 (one-sided).

8.3 Correlative studies

8.3.1 Background

Molecular markers involved in the molecular mechanism of ONC201 will be assessed on available tumor and serum specimens. Urine samples may be used to evaluate the excretion of ONC201 or its metabolites.

8.3.2 Biomarkers

Prolactin and other proteins will be measured in serum as pharmacodynamic markers. One red-top tube (without anti-coagulant) of blood will be collected at the following time points: Baseline and 2 hours, 24 hours, 48 hours, and 72 hours after the first dose of ONC201; Cycle 1 Day 8; Cycle 1 Day 15. An additional 1 tube of 5mL of blood will also be collected on the day of drug administration (pre-dose) on cycles 2, cycle 3 and every odd cycle beyond cycle 3 (day 1 of each cycle). For patients with archival specimens, genomic analysis may also be investigated to determine if a mutation signature profile can help predict safety and/or efficacy

8.3.3 ONC201 Plasma Concentration

The plasma obtained prior to the isolation of PBMCs (see Section 8.3.4) will be used to determine the concentration of ONC201. No additional blood samples will be collected from the patient for these studies. These samples will be used to approximate the Cmax of ONC201 based on its pharmacokinetic profile.

8.3.4 Blood for Immune Cell Studies

Peripheral blood mononuclear cells (PBMCs) will be harvested and investigated for effects of ONC201 on the immune system. One EDTA tube of blood will be collected at the same time points as the red-top tubes are collected: Baseline and 2 hours, 24 hours, 48 hours, and 72 hours after the first dose of ONC201; Cycle 1 Day 8; Cycle 1 Day 15; pre-dose for the first day

of cycle 2 and beyond (day 1 of each cycle). Blood will also be collected at the follow-up visit at the end of treatment, for correlative studies.

Immune cytokines and effectors will be assessed on serum samples obtained for pharmacodynamic analyses. No additional blood samples will be collected from the patient for these studies.

8.3.5 Urine Collection for ONC201 metabolism Studies

An aliquot of the 24 hour baseline urine collection will be needed. The Cycle 1 Day 1 - 24 hour urine collection will be moved to Cycle 1 Day 2. The patients will collect urine in the clinic on Cycle 1 Day 1, starting after taking the first dose of ONC201. The urine will be stored at the site, and the number of hours for this portion of the collection and the volume will be recorded. The patients need to remain in the clinic until the 6 hour PK sample is drawn. The patients will go home with empty bottles provided by the site to finish collecting the 24 hour urine sample and the patient will be told the time of completion and will return the next day. The number of hours for this portion of the collection and the volume will be recorded as well, and 100mL aliquots from both samples will be frozen and transported to Biorepository. On Cycle 1 Day 2 and Day 3, there will be a spot urine.

8.4 EKG Assessments

Triplicate 12-lead EKGs will be performed per the Schedule of Activities and include baseline, cycle 1 day 1, cycle 1 day 15 and cycle 2 day 1, and cycle 2 day 15. Cycle 1 day 1 and cycle 2 day 1 will be obtained at 2 hours (+15 minutes) post-dose. Cycle 1 day 15 and cycle 2 day 15 will be taken pre-dose. Electrocardiogram assessments are to be performed after the measurement of vital signs, with the patient supine and rested for 5 minutes, and before any closely timed blood collection. Two – 5 minutes should lapse between each EKG assessment. The dates and exact times of EKG recordings will be recorded. Any findings from EKGs collected after initiation of study treatment will be captured as AEs if, in the opinion of the investigator, there has been a clinically significant change from baseline.

8.5 Concomitant Medications

Medications used by the patient and therapeutic procedures completed by the patient will be recorded in the CRF from screening through 28 days after the last dose of study drug or the start of subsequent antineoplastic therapy, whichever occurs first.

9 ADVERSE EVENT REPORTING

9.1 Adverse Events

All observed or volunteered adverse events regardless of treatment group or suspected causal relationship to the investigational product(s) will be reported as described in the following sections.

For all adverse events, the investigator must pursue and obtain information adequate both to determine the outcome of the adverse event and to assess whether it meets the criteria for classification as a serious adverse event requiring immediate notification to Oncoceutics. For all adverse events, sufficient information should be obtained by the investigator to determine the causality of the adverse event. The investigator is required to assess causality. For adverse events with a causal relationship to the investigational product, follow-up by the investigator is required until the event or its sequelae resolve or stabilize at a level acceptable to the investigator, and Oncoceutics concurs with that assessment.

All “unexpected” (defined below) and/or “serious” (defined below) adverse events occurring during the active portion of therapy, or up to 30 days after the last dose of treatment, will be reported. Events will be promptly reported, in writing, to the local IRB in accordance with IRB policy. If a death occurs the IRB will be notified within 24-hours of initial receipt of information. All other SAEs must be reported to the IRB within three to ten days of initial receipt of information. Written follow-up reports are required when additional information is needed to fully characterize the event. Copies of each report sent to the IRB will be kept in the study regulatory file.

The principal investigator has the obligation to report all serious adverse events to Oncoceutics (the Sponsor).

This includes serious, related, labeled (expected) and serious, related, unlabeled (unexpected) adverse experiences. All deaths during treatment or within 30 days following completion of active protocol therapy must be reported within 5 working days.

Any serious adverse event occurring after the patient has provided informed consent and until 4 weeks after the patient has stopped study participation must be reported. This includes the period in which the study protocol interferes with the standard medical treatment given to a patient (e.g. treatment withdrawal during washout period, change in treatment to a fixed dose of concomitant medication).

Serious adverse events occurring more than 4 weeks after study discontinuation need only be reported if a relationship to ONC201 study drug (or therapy) is suspected.

For Comparator Drugs/Secondary Suspects (Concomitant Medications), all serious adverse experiences will be forwarded to the product manufacturer by the investigator.

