9.2 Reporting Period

Serious adverse events require immediate notification to Oncoceutics beginning from the time that the patient provides informed consent, which is obtained prior to the patient's participation in the clinical trial, i.e., prior to undergoing any trial-related procedure and/or receiving investigational product, through and including 28 calendar days after the last administration of the investigational product. Any serious adverse event occurring any time after the reporting period must be promptly reported if a causal relationship to investigational product is suspected.

Adverse events (serious and non-serious) should be recorded on the CRF from the time the patient has taken at least one dose of trial treatment through last patient visit.

If a subject begins a new anticancer therapy, the adverse event reporting period for non-serious adverse events ends at the time the new treatment is started. Death must be reported if it occurs during the serious adverse event reporting period after the last dose of investigational product, irrespective of any intervening treatment.

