9.5 Serious Adverse Events

A serious adverse event is any untoward medical occurrence at any dose that:

- Results in death;
- Is life-threatening (immediate risk of death);
- Requires inpatient hospitalization or prolongation of existing hospitalization;
- Results in persistent or significant disability/incapacity;
- Results in congenital anomaly/birth defect.

Progression of the malignancy under trial (including signs and symptoms of progression) should not be reported as a serious adverse event unless the outcome is fatal within the safety reporting period. Hospitalization due to signs and symptoms of disease progression should not be reported as serious adverse event. If the malignancy has a fatal outcome during the trial or within the safety reporting period, then the event leading to death must be recorded as an adverse event and as a serious adverse event with CTC grade 5 (see Section 9.7, Severity Assessment).

Medical and scientific judgment is exercised in determining whether an event is an important medical event. An important medical event may not be immediately life-threatening and/or result in death or hospitalization. However, if it is determined that the event may jeopardize the patient or may require intervention to prevent one of the other outcomes listed in the definition above, the important medical event should be reported as serious.

Examples of such events are intensive treatment in an emergency room or at home for allergic bronchospasm; blood dyscrasias or convulsions that do not result in hospitalization; or development of drug dependency or drug abuse.

The Sponsor will notify the FDA of any adverse experience associated with the use of the drug that is both serious and unexpected, as soon as possible and in no event later than 15 calendar days after the PI's discovery of the event. Notification may be submitted to the Sponsor on a MedWatch Form FDA 3500A <http://www.fda.gov/medwatch/safety/3500a.pdf>.

The PI shall also notify the Sponsor of any unexpected fatal or life-threatening experiences associated with the use of the drug, as soon as possible but no later than 7 calendar days from the PI's discovery of the event information.

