9.12.1 Serious Adverse Event Reporting Requirements

If a serious adverse event occurs, Oncoceutics is to be notified within 24 hours of awareness of the event by the investigator. In particular, if the serious adverse event is fatal or life-threatening, notification to Oncoceutics must be made immediately, irrespective of the extent of available adverse event information. This timeframe also applies to additional new information (follow-up) on previously forwarded serious adverse event reports as well as to the initial and follow-up reporting of Exposure in Utero and exposure during breast feeding cases.

In the rare event that the investigator does not become aware of the occurrence of a serious adverse event immediately (e.g., if an outpatient trial patient initially seeks treatment elsewhere), the investigator is to report the event within 24 hours after learning of it and document the time of his/her first awareness of the adverse event. For all serious adverse events, the investigator is obligated to pursue and provide information to Oncoceutics in accordance with the timeframes for reporting specified above. In addition, an investigator may be requested by Oncoceutics to obtain specific additional follow-up information in an expedited fashion. This information collected for serious adverse events is more detailed than that captured on the adverse event case report form. In general, this will include a description of the adverse event in sufficient detail to allow for a complete medical assessment of the case and

independent determination of possible causality. Information on other possible causes of the event, such as concomitant medications and illnesses must be provided. In the case of a patient death, a summary of available autopsy findings must be submitted as soon as possible to Oncoceutics or its designated representative.

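### Section 9.5 gives the PI up to 7 calendar days to tell the Sponsor of events that Sections 9.2 and 9.12.1 want notified at once, and Section 9.1's 5-working-day limit for deaths names no recipient and fits neither candidate

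*Combined protocol and SAP*

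**What the plan says.** Four places in Section 9 of the combined protocol and SAP set deadlines for the investigator.

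- **Section 9.12.1** gives the investigator 24 hours from awareness to notify the Sponsor of any serious adverse event, and adds that "if the serious adverse event is fatal or life-threatening, notification to Oncoceutics must be made immediately".
- **Section 9.2** agrees: "Serious adverse events require immediate notification to Oncoceutics beginning from the time that the patient provides informed consent". Its period runs to 28 calendar days after the last administration.
- **Section 9.5** says: "The PI shall also notify the Sponsor of any unexpected fatal or life-threatening experiences associated with the use of the drug", and sets the limit as "as soon as possible but no later than 7 calendar days from the PI's discovery of the event information".
- **Section 9.1** contains three relevant statements. Its second paragraph characterises a serious adverse event as one that calls for notifying the company at once. For the IRB it says: "If a death occurs the IRB will be notified within 24-hours of initial receipt of information". Then, shortly after stating the PI's duty to report serious events to the Sponsor, it says: "All deaths during treatment or within 30 days following completion of active protocol therapy must be reported within 5 working days". This last sentence does not say to whom.

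The only precedence rule in the document is in the introduction to Section 7. It places the Schedule of Activities above the text of that section and does not reach Section 9.

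**The concern.** Sections 9.5 and 9.12.1 name the same sender and the same recipient but set different limits, so a difference in recipient cannot explain the gap. The order is also inverted. An ordinary serious event must reach the Sponsor within 24 hours, while an unexpected, drug-associated fatal or life-threatening event carries an outer limit of 7 days in Section 9.5.

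At stake is how soon the Sponsor learns of events that bear on trial decisions. Section 3.3 de-escalates when more than 1 of 6 patients in the first Phase 1 cohort has a DLT. Under Section 5.6, a possibly related non-hematologic event of Grade 3 or higher within 21 days is generally a DLT. With numbers that small, one event can decide a cohort. Section 5.4 lets the Sponsor end the study if other enrolled patients suffer severe or life-threatening toxicity.

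**Working it through.** The plan gives no statistical figure to reproduce here. The check sets the deadlines side by side and converts them to a common unit.

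**Step 1: which rules apply to which event.** Any event resulting in death is serious under Section 9.5, so Section 9.12.1 applies to every death.

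| Event | 9.1: 5 working days | 9.5: 7 calendar days | 9.2 and 9.12.1: immediate | Limits disagree? |
|---|---|---|---|---|
| Death, unexpected and drug-associated | yes | yes | yes | yes, all three |
| Death, expected or not drug-associated | yes | no | yes | yes, if 9.1 means the Sponsor |
| Life-threatening, not fatal, unexpected and drug-associated | no | yes | yes | yes, 9.5 against the rest |
| Life-threatening, not fatal, expected or not drug-associated | no | no | yes | no |

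The comparison with Section 9.2 holds within its 28-day period. Section 9.1 counts 30 days for deaths. Section 9.12.1 states no window of its own.

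**Step 2: the recipient of the 5-working-day sentence.** There are two candidates.
- Sponsor: 5 working days against immediately (Sections 9.2 and 9.12.1). Conflict.
- IRB: 5 working days against 24 hours for a death (Section 9.1 itself). Conflict.

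The sentence needs correction under either reading.

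**Step 3: size of the gap.**
- Immediate (day 0) to the 9.5 limit: 7 − 0 = 7 calendar days.
- The 24-hour rule to the 9.5 limit: 7 − 1 = 6 calendar days.
- Five working days in calendar days: awareness on Monday to Friday crosses one weekend, 5 + 2 = 7. Awareness on Saturday ends the following Friday, 6 days. Awareness on Sunday ends the following Friday, 5 days.
- If one public holiday falls in the window (an assumption), the range becomes 8 to 10 days, depending on the weekday.

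**Step 4: what fits inside the gap.**
- Section 7.3 schedules ONC201 on days 1, 8 and 15 of a 21-day cycle. The spacing is 7 days, so a 7-day interval contains one scheduled dose for each patient on uninterrupted weekly treatment.
- Section 9.5 gives the Sponsor 15 calendar days, counted from the PI's discovery, to notify the FDA of a serious and unexpected event. A report on day 7 leaves 15 − 7 = 8 days.

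**Step 5: link to the safety boundaries.** Section 10.3 acts when 4 of 12 or 6 of 26 patients discontinue drug for treatment-related adverse events. Its count is of discontinuations, not of serious-event reports, so the reporting limits do not enter it directly.

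**The case against.** The best defence is that the limits are compatible ceilings. Section 9.5 asks for notice as soon as possible and words it as an additional duty. A site that obeys Section 9.12.1 meets every Sponsor limit, and neither Section 9.5 nor Section 9.1 releases it from Sections 9.2 and 9.12.1. Section 9.1 opens by referring forward to the sections that follow, and Section 9.10 sends serious-event withdrawals to the requirements below it. The title of Section 9.12.1 makes it the natural destination. The IRB, which may stop the trial under Section 5.5, is to hear of a death within 24 hours in any case.

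Much of this stands. Delay is possible, not built in, and a death need not go without oversight for a week. But the forward reference does not settle the matter, because Section 9.5 is itself one of the sections that follow. A site reporting on day 6 could still point to Section 9.5 as its authority. The 24-hour IRB rule covers deaths only, so it does not help with non-fatal life-threatening events.

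A reader might infer more than the text supports, in three ways:
- That three deadlines compete for every death or life-threatening event. They meet only on an unexpected, drug-associated death; the 5-working-day sentence covers deaths alone, and its recipient is inferred only from its position.
- That the Section 10.3 stopping rule is delayed. Those boundaries count discontinuations, and the documents do not tie them to the reporting limits.
- That the Sponsor would miss its FDA limit. A day-7 report leaves 8 days, and no breach is shown.

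**Conclusion.** The inconsistency is real and should be corrected. The firm part is Section 9.5 against Sections 9.2 and 9.12.1: same sender, same recipient, limits up to 7 calendar days apart (6 if measured from the 24-hour rule), for unexpected, drug-associated fatal or life-threatening events. The second part is the 5-working-day sentence for deaths in Section 9.1, usually equal to 7 calendar days, which is inconsistent with another rule whichever recipient is meant.

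The consequence is a delay that a site could defend by citing one section, long enough to include one weekly dose and to postpone a DLT-based dose decision or the Sponsor's choice to stop. It rests on a site relying on the longer limit despite Sections 9.2 and 9.12.1. The documents give no basis for saying how often that would happen or which decision would change. No endpoint, sample size, power figure or analysis is affected.

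**What to change.** Reconcile the passages to one investigator-to-Sponsor deadline. Have Sections 9.1 and 9.5 refer to Section 9.12.1, which already agrees with Section 9.2, and remove the 7-calendar-day and 5-working-day limits for that recipient. If the 5-working-day limit is meant for someone other than the Sponsor, name that recipient; if it is the IRB, reconcile it with the 24-hour rule in the same section.

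The same edit should align the reporting windows, which now read 30 days after active therapy and 4 weeks after stopping participation (Section 9.1) and 28 days after the last administration (Section 9.2).

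The cost is a wording amendment. Sites take on no new reporting burden to the Sponsor, because Sections 9.2 and 9.12.1 already require the fast report.

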9.2 Reporting Period

Serious adverse events require immediate notification to Oncoceutics beginning from the time that the patient provides informed consent, which is obtained prior to the patient's participation in the clinical trial, i.e., prior to undergoing any trial-related procedure and/or receiving investigational product, through and including 28 calendar days after the last administration of the investigational product. Any serious adverse event occurring any time after the reporting period must be promptly reported if a causal relationship to investigational product is suspected.

Adverse events (serious and non-serious) should be recorded on the CRF from the time the patient has taken at least one dose of trial treatment through last patient visit.

If a subject begins a new anticancer therapy, the adverse event reporting period for non-serious adverse events ends at the time the new treatment is started. Death must be reported if it occurs during the serious adverse event reporting period after the last dose of investigational product, irrespective of any intervening treatment.

9.3 Definition of an Adverse Event

An adverse event is any untoward medical occurrence in a clinical investigation patient administered a product or medical device; the event need not necessarily have a causal relationship with the treatment or usage. Examples of adverse events include but are not limited to:

- Abnormal test findings;
- Clinically significant symptoms and signs;
- Changes in physical examination findings;
- Hypersensitivity.

Additionally, they may include the signs or symptoms resulting from:

- Drug overdose;
- Drug withdrawal;
- Drug abuse;
- Drug misuse;
- Drug interactions;
- Drug dependency;
- Exposure in utero;
- Exposure during breast feeding.

Worsening of signs and symptoms of the malignancy under trial should be reported as adverse events in the appropriate section of the CRF. Disease progression assessed by measurement of malignant lesions on radiographs or other methods should not be reported as adverse events

